### 6.1.1. Administration

Study interventions will be administered orally and according to the conditions described in the [SoA](#) section and Protocol [Section 5.3.2 Meals and Dietary Restrictions](#).

On Period 1 Day 1, following an overnight fast of at least 10 hours, participants will receive PF-07817883 300 mg administered orally in the morning of Period 1 Day 1.

Coadministration: On Period 2 Day 4, the dose of PF-07817883 300 mg should be administered following an overnight fast of at least 10 hours and immediately after the administration of the dose of itraconazole 200 mg. Investigator site personnel will administer PF-07817883 with ambient temperature water to a total volume of approximately 240 mL. On Period 2 Days 1 through 7, participants will receive itraconazole 200 mg (in a 20-mL solution) QD orally. Investigator site personnel will administer itraconazole with ambient temperature water to a total volume of approximately 240 mL.

Administration of study intervention(s) at the site will be performed by an appropriately qualified and trained member of the study staff as allowed by local, state, and institutional guidance.

Following administration of study intervention(s) at the site, participants will be observed for 1 hour by an appropriately qualified and trained member of the study staff. Appropriate medication and other supportive measures for management of a medical emergency will be available in accordance with local guidelines and institutional guidelines.

### 6.2. Preparation, Handling, Storage, and Accountability

1. The investigator or designee must confirm that appropriate conditions (eg, temperature) have been maintained during transit for all study interventions received and any discrepancies are reported and resolved before use of the study intervention.
2. Only participants enrolled in the study may receive study intervention and only authorized site staff may supply, prepare, and/or administer study intervention.
3. All study interventions must be stored in a secure, environmentally controlled, and monitored (manual or automated recording) area in accordance with the labeled storage conditions with access limited to the investigator and authorized site staff. At a minimum, daily minimum and maximum temperatures for all site storage locations must be documented and available upon request. Data for nonworking days must indicate the minimum and maximum temperatures since previously documented upon return to business.
4. Any excursions from the study intervention label storage conditions should be reported to Pfizer upon discovery along with actions taken. The site should actively pursue options for returning the study intervention to the labeled storage conditions, as soon as possible. Once an excursion is identified, the study intervention must be quarantined and not used until Pfizer provides permission to use the study intervention. Specific details regarding the excursion definition and information to

report for each excursion will be provided to the site in the PCRU local/site procedures.

5. Any storage conditions stated in the SRSD will be superseded by the storage conditions stated on the label.
6. Study interventions should be stored in their original containers.
7. The investigator, institution, head of the medical institution (where applicable), or authorized site staff is responsible for study intervention accountability, reconciliation, and record maintenance (ie, receipt, reconciliation, and final disposition records), such as the IPAL or sponsor-approved equivalent. All study interventions will be accounted for using a study intervention accountability form/record.
8. Further guidance and information for the final disposition of unused study interventions are provided in the PCRU's local/site procedures. All destruction must be adequately documented. If destruction is authorized to take place at the investigator site, the investigator must ensure that the materials are destroyed in compliance with applicable environmental regulations, institutional policy, and any special instructions provided by Pfizer.

Upon identification of a product complaint, notify the sponsor within 1 business day of discovery.

#### **6.2.1. Preparation and Dispensing**

Within this protocol, preparation refers to the investigator site activities performed to make the study intervention ready for administration or dispensing to the participant by qualified staff. Dispensing is defined as the provision of study intervention, concomitant treatments, and accompanying information by qualified staff member(s) to a healthcare provider or participant in accordance with this protocol. Local health authority regulations or investigator site guidelines may use alternative terms for these activities.

See the PCRU local/site procedures for PF-07817883 for instructions on how to prepare the study intervention for administration. Commercial itraconazole (eg, Sporanox® or an equivalent generic product) oral solution will be dispensed at the PCRU into oral syringes using the package insert as guidance. All study intervention should be prepared and dispensed by an appropriately qualified and experienced member of the study staff (eg, physician, nurse, physician's assistant, nurse practitioner, pharmacy assistant/technician, or pharmacist) as allowed by local, state, and institutional guidance. A second staff member will verify the dispensing.

#### **6.3. Assignment to Study Intervention**

The investigator will assign participant numbers to the participants as they are screened for the study.

#### **6.4. Blinding**

This is an open-label study.

#### **6.5. Study Intervention Compliance**

When participants are dosed at the site, they will receive study intervention directly from the investigator or designee, under medical supervision. Study site personnel will examine each participant's mouth to ensure that the study intervention was ingested.

#### **6.6. Dose Modification**

No dose modification is anticipated.

#### **6.7. Continued Access to Study Intervention After the End of the Study**

No study intervention will be provided to participants at the end of their study participation.

#### **6.8. Treatment of Overdose**

For this study, any dose of PF-07817883 and itraconazole greater than **CCI** mg and 400 mg, respectively, within a 24-hour time period  $\pm 2$  hours will be considered an overdose.

There is no specific treatment for an overdose.

In the event of an overdose, the investigator should:

1. Contact the study medical monitor within 24 hours.
2. Closely monitor the participant for any AEs/SAEs and laboratory abnormalities as medically appropriate and follow-up until resolution, stabilization, the event is otherwise explained, or the participant is lost to follow-up (as defined in Section [7.3](#)).
3. Document the quantity of the excess dose as well as the duration of the overdose in the CRF.
4. Overdose is reportable to Pfizer Safety **only when associated with an SAE**.
5. Obtain a blood sample for PK analysis within 1 day from the date of the last dose of study intervention if requested by the study medical monitor (determined on a case-by-case basis).

Decisions regarding dose interruptions or modifications will be made by the investigator in consultation with the study medical monitor as needed based on the clinical evaluation of the participant.

#### **6.9. Prior and Concomitant Therapy**

Use of prescription or nonprescription drugs and dietary and herbal supplements are prohibited within 28 days or 5 half-lives (whichever is longer) prior to the first dose of study intervention. Limited use of nonprescription medications that are not believed to affect

participant safety or the overall results of the study may be permitted on a case-by-case basis following approval by the sponsor. Acetaminophen/paracetamol may be used at doses of  $\leq 1$  g/day.

Hormonal contraceptives that meet the requirements of this study are allowed to be used in participants who are WOCBP (see [Appendix 4](#)).

All concomitant treatments taken during the study must be recorded with indication, daily dose, and start and stop dates of administration. All participants will be questioned about concomitant treatment at each clinic visit.

Treatments taken within 28 days before the first dose of study intervention will be documented as a prior treatment. Treatments taken after the first dose of study intervention will be documented as concomitant treatments.

#### **6.9.1. Rescue Medicine**

There is no rescue therapy to reverse the AEs observed with PF-07817883 or itraconazole. Standard medical supportive care must be provided to manage the AEs.

### **7. DISCONTINUATION OF STUDY INTERVENTION AND PARTICIPANT DISCONTINUATION/WITHDRAWAL**

#### **7.1. Discontinuation of Study Intervention**

It may be necessary for a participant to permanently discontinue study intervention. Reasons for permanent discontinuation of study intervention include the following:

- AE requiring discontinuation in the investigator's view,
- Pregnancy,
- Positive COVID-19 test.

If study intervention is permanently discontinued, the participant will not remain in the study for further evaluation. See the [SoA](#) for data to be collected at the time of discontinuation of study intervention.

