Participants will receive itraconazole 200 mg, administered orally QD on Period 2 Days 1 through 7 (Study Days 5-11), inclusive. On Period 2 Day 1 the itraconazole dosing will take place approximately 1 hour following the last PK sample collection on that day (96 hours post-dose time point). On Period 2 Day 4 (Study Day 8), participants will receive PF-07817883 300 mg administered orally immediately after the itraconazole dose for that day, after which the participants will undergo serial PK sampling up to 96 hours and urine will be collected up to 24 hours following the PF-07817883 dose on Period 2 Day 4. As a result, the washout interval between dosing of PF-07817883 in Period 1 and Period 2 is 7 days. Participants may be confined at the PCRU during the entire duration of the study, and they will be discharged from the PCRU on Period 2 Day 8 (Study Day 12) following completion of all assessments.

The participants will be fasted overnight for at least 10 hours before administration of PF-07817883 (Period 1 Day 1 [Study Day 1] and Period 2 Day 4 [Study Day 8]). Details of meal and water restrictions along with other necessities are elaborated in Section 5.3 Lifestyle Considerations.

If a participant has any clinically significant, study-related abnormalities at the conclusion of a scheduled inpatient portion of the study, the Pfizer medical monitor (or designated representative) should be notified and the participant may be asked to remain in the PCRU until such abnormalities are deemed not clinically significant, or it is safe for outpatient follow-up.

A follow-up (which may be a phone call) will be made to participants approximately 28 to 35 days from administration of the final dose of study intervention.

The total planned duration of participation, from the Screening visit to the last follow-up, is approximately 13 weeks.

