### **7.2. Participant Discontinuation/Withdrawal From the Study**

A participant may withdraw from the study at any time at their own request. Reasons for discontinuation from the study include the following:

- Refused further study procedures,
- Lost to follow-up,
- Death,

- Study terminated by the sponsor,
- Investigator's decision,
- Pregnancy.

At the time of discontinuing from the study, if possible, an early discontinuation visit should be conducted. See the [SoA](#) for assessments to be collected at the time of study discontinuation and follow-up and for any further evaluations that need to be completed.

The early discontinuation visit applies only to participants who are enrolled/randomized and then are prematurely withdrawn from the study. Participants should be questioned regarding their reason for withdrawal.

The participant will be permanently discontinued from the study intervention and the study at that time.

If a participant withdraws from the study, they may request destruction of any remaining samples taken and not tested, and the investigator must document any such requests in the site study records and notify the sponsor accordingly.

If the participant withdraws from the study and also withdraws consent (see Section 7.2.1) for disclosure of future information, no further evaluations will be performed and no additional data will be collected. The sponsor may retain and continue to use any data collected before such withdrawal of consent.

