### **7.2.1. Withdrawal of Consent**

Participants who request to discontinue receipt of study intervention will remain in the study and must continue to be followed for protocol-specified follow-up procedures. The only exception to this is when a participant specifically withdraws consent for any further contact with them or persons previously authorized by the participant to provide this information. Participants should notify the investigator in writing of the decision to withdraw consent from future follow-up, whenever possible. The withdrawal of consent should be explained in detail in the medical records by the investigator, as to whether the withdrawal is only from further receipt of study intervention or also from study procedures and/or posttreatment study follow-up, and entered on the appropriate CRF page. In the event that vital status (whether the participant is alive or dead) is being measured, publicly available information should be used to determine vital status only as appropriately directed in accordance with local law.

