#### **8.4.1. Time Period and Frequency for Collecting AE and SAE Information**

The time period for actively eliciting and collecting AEs and SAEs (“active collection period”) for each participant begins from the time the participant provides informed consent, which is obtained before undergoing any study-related procedure and/or receiving study intervention), through and including a minimum of 28 calendar days, except as indicated below, after the last administration of the study intervention.

Follow-up by the investigator continues throughout the active collection period and until the AE or SAE or its sequelae resolve or stabilize at a level acceptable to the investigator.

When a clinically important AE remains ongoing at the end of the active collection period, follow-up by the investigator continues until the AE or SAE or its sequelae resolve or stabilize at a level acceptable to the investigator and Pfizer concurs with that assessment.

For participants who are screen failures, the active collection period ends when screen failure status is determined.

If the participant withdraws from the study and also withdraws consent for the collection of future information, the active collection period ends when consent is withdrawn.

If a participant permanently discontinues or temporarily discontinues study intervention because of an AE or SAE, the AE or SAE must be recorded on the CRF and the SAE reported using the CT SAE Report Form.

Investigators are not obligated to actively seek information on AEs or SAEs after the participant has concluded study participation. However, if the investigator learns of any SAE, including a death, at any time after a participant has concluded study participation, and they consider the event to be reasonably related to the study intervention, the investigator must promptly report the SAE to Pfizer using the CT SAE Report Form.

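### Protocol Section 7.1 removes anyone who permanently stops study intervention from the study; this contradicts Section 7.2.1 for participant-requested stops and sits badly with the 28-day AE collection in Section 8.4.1

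*Protocol*

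**What the plan says.** Protocol Section 7.1 gives reasons for permanent discontinuation as an open list (adverse event, pregnancy, positive COVID-19 test) and then states: "If study intervention is permanently discontinued, the participant will not remain in the study for further evaluation". The next sentence refers to the Schedule of Activities (SoA) for data to collect at the time of stopping.

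Section 7.2.1 states: "Participants who request to discontinue receipt of study intervention will remain in the study and must continue to be followed for protocol-specified follow-up procedures". It adds: "The only exception to this is when a participant specifically withdraws consent for any further contact with them", or with persons the participant had authorised to give information.

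Section 8.4.1 sets the active AE and SAE collection period for each participant from consent "through and including a minimum of 28 calendar days, except as indicated below, after the last administration of the study intervention". Two early endings follow. One is screen failure. The other applies when a participant "withdraws from the study and also withdraws consent for the collection of future information, the active collection period ends when consent is withdrawn". The same section says that investigators have no duty to look actively for events after participation has concluded.

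Section 7.2, on leaving the study, refers to the SoA "for assessments to be collected at the time of study discontinuation and follow-up and for any further evaluations that need to be completed". Where consent is also withdrawn "for disclosure of future information, no further evaluations will be performed and no additional data will be collected".

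Section 4.1 says that a follow-up, possibly by phone, "will be made to participants approximately 28 to 35 days from administration of the final dose of study intervention".

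SAP Section 3.5.1 counts follow-up events up to 35 days after the last dose as treatment emergent.

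**The concern.** The sentence in 7.1 covers every permanent stop, whatever the reason. It therefore reaches the participant who asks to stop, and Section 7.2.1 gives that participant the opposite instruction.

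For a stop decided by the investigator, for example because of an adverse event, 7.2.1 does not apply. The issue there is how 7.1 combines with 8.4.1. If 7.1 ends participation at the early-termination visit, a site could conclude that it no longer has to look for new events, although the 28-day minimum has not run out.

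Safety and tolerability is a secondary objective, and someone who stopped because of an adverse event is a participant whose late course matters. An event that nobody asks about cannot enter the SAP's treatment-emergent summaries.

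**Working it through.** The plan states no figure to reproduce. The check is a comparison of texts, followed by simple study-day arithmetic.

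**Step 1. Participant-requested stops.**
- 7.1: a permanent stop means that the participant does not remain in the study for evaluation. No exception is given, and the list of reasons is open.
- 7.2.1: a requested stop means that the participant remains and must be followed. The one exception is withdrawn consent for contact.
- For a participant who asks to stop and still agrees to be contacted, the two rules conflict directly.

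**Step 2. Stops because of an adverse event or pregnancy.**
- 8.4.1 gives each participant at least 28 days of collection after the last dose. Its early endings are screen failure, and study withdrawal together with withdrawn consent. Stopping study intervention is not among them.
- 8.4.1 also removes the duty to look actively for events once participation has concluded. After that, the investigator must report only SAEs that come to light and are judged reasonably related.
- Whether the 28-day duty survives therefore depends on whether 7.1 concludes participation. Its literal wording suggests that it does. The minimum in 8.4.1 suggests that it does not. This is an inconsistency that a careful site could resolve.

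**Step 3. Which text points to follow-up.**
- 7.2 refers those who leave early to the SoA for follow-up, and rules out further evaluation only when consent is also withdrawn.
- 4.1 times the follow-up contact from the final dose, not from completion of both periods.
- The SoA for Period 2 (Table 3) schedules AE monitoring at that follow-up.

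**Step 4. What is scheduled after a stop.** Planned dosing days are Study Day 1 and Study Days 5 to 11. Minimum collection ends on last-dose day + 28. The contact window is last-dose day + 28 to last-dose day + 35.

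| Last dose | Minimum collection ends | Contact window |
|---|---|---|
| Day 1 (early stop) | 1 + 28 = Day 29 | Days 29 to 36 |
| Day 5 (early stop) | 5 + 28 = Day 33 | Days 33 to 40 |
| Day 10 (latest early stop) | 10 + 28 = Day 38 | Days 38 to 45 |
| Day 11 (completer) | 11 + 28 = Day 39 | Days 39 to 46 |

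A completer is discharged on Day 12 and then has one scheduled contact. A participant who stops early and leaves the unit would, under the same schedule, also have one. That contact is what a literal reading of 7.1 puts at risk.

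**Step 5. How many participants.** The documents give no rate of treatment stops. As an assumption, take 0 to 2 of 12, where 2 is the planned dropout reserve (12 − 10). That gives 0 to 2 contacts. The reserve is a dropout allowance and not a rate of treatment stops, and it would include people who withdraw consent, for whom no contact is due.

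**The case against.** The strongest reply is that the phrase about further evaluation in 7.1 can be read as confinement, dosing and PK procedures only. On that reading, leaving the study can coexist with 28 days of AE collection, because 8.4.1 ends collection early only when consent is withdrawn as well. This reply stands for stops because of an adverse event or pregnancy, which is why that part is called an inconsistency. It does not reconcile 7.1 with 7.2.1, where one text says that the participant does not remain in the study and the other says that the participant does.

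It can also be argued that 7.2.1 is the outlier. Section 7.2 says that a participant who discontinues from the study leaves both intervention and study at that point, which pairs the two as 7.1 does. The documents do not state which rule governs. However, that sentence concerns people leaving the study, and the same section still sends them to the SoA for follow-up.

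Much of the safety risk is covered elsewhere. Known events are followed to resolution or stabilisation (8.4.1, 8.4.3) and pregnancies to their outcome (8.4.5.1). Suspected kidney injury (7.1.1) and liver injury (Appendix 6) call for a return visit. What remains exposed is a new event that does not otherwise come to the site's attention.

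A reader might also see a contradiction between the COVID-19 entry in the 7.1 list and the instruction in 7.1.3 to continue treatment unless there is a safety concern. The documents do not support that. Section 7.1 says only that stopping may be necessary, and 7.1.3 is its own subsection and supplies the rule.

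**Conclusion.** The point holds and is minor. For participant-requested stops, 7.1 and 7.2.1 contradict each other. For stops because of an adverse event or pregnancy, 7.1 is inconsistent with 8.4.1, and a literal reading could end the search for new events at the early-termination visit.

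The size is one contact at 28 to 35 days per affected participant, plus any new event it would have found. This assumes a site that follows 7.1 literally. With 0 to 2 such participants, itself an assumption, it means 0 to 2 contacts.

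Two stronger readings should be resisted. A reader might infer that nearly the whole 28-day collection period is lost. That would require a site to set aside 8.4.1, 7.2 and the SoA follow-up column, and even completers have only one scheduled contact after discharge. A reader might also infer damage to the primary result. The conflict concerns safety follow-up, and it leaves the primary PK analysis unaffected.

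**What to change.** Replace the sentence in Protocol Section 7.1 with:

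> Participants who permanently discontinue study intervention will receive no further dosing, will complete the early-termination assessments, and will remain for safety follow-up through the 28-35 day contact unless they withdraw consent for further contact.

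This brings 7.1 into line with 7.2.1, 7.2 and 8.4.1, and lets the SAP's 35-day counting rule work for participants who stop early. The SAP needs no change.

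The cost is one reworded sentence and at most one extra contact, possibly a phone call, for each participant who stops. No additional participants or PK samples are needed.
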